Clinical Trial Protocol

Title of study: Skin Tag Removal Device; A Clinical Study to Determine Outcomes of Treating Adults with Acrochordons (Skin Tags)

NCT06463613

Date: 06/05/2025

Clinical Investigation Protocol

Title: Skin Tag Removal Device; A Clinical Study to Determine

Outcomes of Treating Adults with Acrochordons (Skin Tags)

Protocol: UKI-001

Sponsor: UK Innovations GP LTD

Version: 2

Date: TBD

Confidentiality Statement

This document contains confidential information that must not be disclosed to anyone other than the Sponsor, the Investigator Team, HRA, host organization, and members of the Research Ethics Committee and Regulatory Authorities unless authorized to do so.

Trial Title:	Skin Tag Removal Device; A Clinical Study to Determine Outcomes of Treating

Adults with Acrochordons (Skin Tags)

Protocol Number: UKI-001

Protocol Version: 2

Protocol Date: TBD

Protocol signature page

The undersigned has read and understood the trial protocol detailed above and agrees to conduct the trial in compliance with the protocol.

Principal Investigator Name	Principal Investigator Signature	Date	
(Please print)			

Protocol Section	Protocol Version 1	Protocol Version 2	Rationale
Section 3.1-3.2, 4, 6.2.1-6.2.3	Use of micro STR on 2-4 mm skin tags	Use of micro STR on approximately 4-6mm skin tags	The micro STR band has not reached the desired level of efficacy on 2-4mm skin tags per use under protocol version 1. The Sponsor recommends the use of a micro STR band to be placed on larger skin tags, 4-6mm, where they may be more effective at restricting blood flow to the skin tag and removing the tag.
Section 6.2.4, 6.2.6	Daily eDiaries Day 1-10	Daily eDiaries at screening visit, Day 1-20	An eDiary has been added to the screening visit to capture a photo of the skin tag at the time of banding. The number of daily diaries have been extended to 20 days to allow tracking for skin tags which may fall off after day 10.
Section 6.2.4	Virtual Visit 2 window Day 5-8	Virtual Visit 2 window Day 5-9	Visit window was extended to allow for more time to conduct the visit with no impact to patient safety
Section 6.2.4	Virtual Visit 3 window Day 11-14	Virtual Visit 3 window Day 21-24	The visit was moved to one day after the last daily diary completed by participants, which is now day 20 under protocol version 2.

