2.2. Purpose of Investigative Study

The aim of this study is to investigate the safety and effectiveness of a mechanical device to remove skin tags in adults. The device utilizes the ligation method by applying a silicone band around the base of a skin tag, therefore restricting the blood supply, which is vital to its growth and survival. Because this method does not include freezing or burning of tissue in or around the skin tag, it could be considered less invasive and less risky than other options.

A clinical validation study to demonstrate the safe and effective removal of skin tags will be completed under the direction of an investigator (dermatologist or other health care professional) led protocol. This study will assess the proportion of skin tags successfully removed within a 20-day period, and to evaluate associated safety outcomes. Adult (22 years and above) subjects fitting the inclusion/exclusion criteria will be recruited, given they have one or more skin tags consistent with device labeling. All subjects entering the clinical study will have the device applied by the healthcare professional and proceed through the study, recording their experience using an electronic clinical diary to collect data.

Since this device is to be sold over-the-counter, evaluation of the subject's self-selection and label comprehension abilities will be completed under a separate Human Factors and Usability study and is therefore not required in the scope of this clinical trial.

3

³ UC Davis Dermatology Online Journal

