Once the band has been placed, the Investigator will examine the skin tag, complete study documentation, and answer any questions or concerns the subject has regarding the device or procedure. A small adhesive bandage will be placed over each treated skin tag immediately following banding. The subject will then review trial diary instructions, including but not limited to the documentation of all observable characteristics regarding the banded skin tag(s). The subject will complete their first eDiary at the visit including photo upload(s) of the banded skin tags. They will continue eDiary completion every evening starting at Day 1 through Day 20. This diary is electronic (eDiary) and accessed through the CRO's secure website. All subjects must be able to access the eDiary via smartphone to participate in the study, as defined in the informed consent. per day for eDiary completion, up to a maximum of \$200.

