6.2.4. Schedule of Events

Potential participants may self-complete an IRB-approved online pre-screening survey. Those eligible based on survey responses will meet with the study team & Principal Investigator for the screening and baseline visit. If the subject agrees to take part in the study, they must read and sign a consent form, which will include the Inclusion/Exclusion criteria, information on completing the study

diary electronically as well as the covered medical expenses by the clinical study (see 6.2.5).

Schedule of Events

	Pre-Screening Phase	Treatment Phase		Post-Treatment	Unscheduled	
		Visit 1	Visit 2	Visit 3	Visit 4	Unscheduled
Visit Type	Pre-Screening	Screening/ Baseline	Follow-Up	Follow-Up	End of Study	Unscheduled
Visit Location	(virtual)	(in clinic)	(virtual)	(virtual)	(virtual)	(in clinic)
Window	(-42 to Day 1)	Day 1	Days 5-9	Days 21-24	Days 30-37	N/A
Procedure						
Pre-Screening Survey	Х					
Informed Consent		Х				
Demographics		Х				
Medical History		Х				
Concomitant Medications		Х	Х	Х	Х	
Modified Fitzpatrick Skin Type		Х				
Limited Dermatological Exam		Х				Х
Eligibility Determination		Х				
Device Use/ Band Application4		Х				
Band Re-application(s)		X _e				
eDiary Training		Х				
eDiary/Photo Review		х	Х	X¹	X ²	
Adverse Events		Х	Х	Х	Х	Х
Surgical Excision						X ³

¹ if treated skin tag(s) has/have not fallen off by Visit 3, participant has option to have skin tag(s) removed at an Unscheduled Visit by calling the Investigator's office and making an appointment

² no eDiary entries for this visit; only photo(s) to be submitted by participant and reviewed by Investigator to confirm coordinator may exit participant from study. If Investigator has concerns about participant's D30 photo, participant will have an Unscheduled Visit for examination

³ optional: presented to subject in the event the skin tag was not removed by STR study device by D10

⁴ Participants will complete the initial eDiary and photo(s) upload at the Day 1, in-clinic visit.

⁵ Band -Repplication to be performed by PI or Sub-I as needed at the site in the event of the band falling off. Participants will be allowed 2 reapplications per skin tag throughout the course of the study.

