	Visit 3 (virtual)	The subject is to complete a virtual visit where the following activities are performed: • General observations, as described by the subject, of the skin tag site. • Review photos uploaded to eDiary and discuss any issues with irritation, infection, or other adverse events • If skin tag(s) has/have not been removed by STR study device, study team member to review options with subject for tag removal. • If subject wants skin tag to be removed, study team member instructs them to call Investigator's office for an Unscheduled Visit to have skin tag removed by Investigator • If subject is not interested in skin tag removal by Investigator, study team member instructs them to follow directions provided on After Care Instructions on proper self-removal of the band around treated skin tag • Study team member to review AEs and Concomitant Medications at virtual visit • Study team member and subject to review After Care Instructions that are to be followed until Visit 4 (and beyond if	

	necessary). Study team member to remind subject that an in-clinic visit is always available upon request, up to Visit 4, and to call with any questions or concerns
Visit 4 (virtual)	The subject is to complete a remote visit where the following activities are performed: • Photo submission(s) of skin tag site(s) approximately 30 days (but not earlier than Day 30) after band(s) was/were placed • Investigator will review photo(s) and verify the subject is either cleared to exit study or needs to return to clinic for an Unscheduled Visit • Study team member to review AEs and Concomitant Medications at virtual visit once subject is cleared to exit study by Investigator

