6.2.6.1. Reported Post Study Data

Case Report Forms will be used by the CRO to collect and organize data. All data collected during the investigational study will be compiled by the CRO and securely stored by the Sponsor. Data collected will be captured and archived using a per-protocol approach.

The following table provides a list of the reported primary outcomes, as evidenced by the study. Data subgroup analysis following the completion of the study and performance data analysis reported by:

- Age (22-50 vs. 51+)
- Sex assigned at birth (M/F)
- Band size (micro vs. standard)
- Band detachment events, including duration of detachment
- Body location of band placement
- Mechanism of device used (automatic vs. manual)

Data Collected	Description
Proper band placement	Source: Visit 1, Investigator Records STR study device bands will be placed on up to two (2) skin tag(s) by the Investigator. Source: eDiary Participant will upload a photo(s) of the banded skin tag(s) in the eDiary at the Visit 1 in-clinic visit.

Efficacy of skin tag removal	Source: Days 2-2 O, Case Report Forms and Subject eDiary The total number of skin tags treated and those successfully removed by use of the STR study device will be compiled and reported. In all cases, the removal rate will be categorized by skin tag size (micro or standard) and body location as well as subject demographics
Safety and Potential Health Impacts	Source: Case Report Forms and Subject eDiary There are not any serious adverse effects anticipated with this study potential non-serious side effects during the use of the STR study device are as follows and will be collected: Irritation Tenderness Pigment change Scarring Less common but potential side effects that need to be collected and addressed are: Infection Redness or swelling at the base of tag Bleeding Pain Delayed healing (greater than 14 days after tag falling off/removal) Hypertrophic or Keloid scarring Other (as defined/described in the eDiary manual) General use comments by the subjects, including photos depicting the progression of the skin tag(s) treatment and after the tag has fallen of Only adverse events associated with the device will be recorded and documented as Adverse Device Effects (ADEs).

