9.2. Adverse Device Effect (ADE)

An Adverse Device Effect is an AE related to the use of an investigational medical device. For this study, the following ADEs will be collected if they occur at the location of the skin tag removal band placement including, but not limited to:

- Irritation
- Pain
- Bleeding
- Infection
- Hypertrophic or keloid scarring

- Prolonged healing, defined as the healing process taking longer than 14 days after the tag has fallen off or been removed by the Investigator
- Any other symptom or abnormality that led to permanent discontinuation of the trial device.

These events will be rated a mild, moderate or severe intensity using the following definitions:

Mild: Mild events are usually transient and do not interfere with the Participant's daily activities

Moderate: Moderate events introduce a low level of inconvenience or concern to the Participant and may interfere with daily activities. A medication may be necessary.

Severe: Severe events interrupt the Participant's usual daily activity

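### Prolonged healing is counted from tag loss but the last scheduled visit from banding, so late-lost or excised tags still unhealed at Visit 4 may not be classifiable there

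*Protocol*

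**What the plan says.** Section 9.2 includes among the adverse device effects to be collected: "Prolonged healing, defined as the healing process taking longer than 14 days after the tag has fallen off". Removal by the Investigator starts the same 14-day count. The data table in Section 6.2.6.1 repeats the threshold: "Delayed healing (greater than 14 days after tag falling off/removal".

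The last scheduled assessment is Visit 4, a virtual visit. The schedule in Section 6.2.4 places it on Days 30-37, and Section 6.2.6 asks for a photo "approximately 30 days (but not earlier than Day 30) after band(s) was/were placed". The schedule adds that there are "no eDiary entries for this visit; only photo(s) to be submitted by participant"; adverse events are also reviewed at that visit. The Investigator then either clears the participant to leave the study or asks for an Unscheduled Visit.

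Late tag loss is expected. Section 2.2 gives the aim as the "proportion of skin tags successfully removed within a 20-day period". The table of changes explains: "The number of daily diaries have been extended to 20 days to allow tracking for skin tags which may fall off after day 10". Section 6.2.3 allows up to two rebandings per tag, which can delay loss. If the tag is still there at Visit 3 (Days 21-24), removal by the Investigator is offered.

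On the diary, Section 6.2.1 says: "They will continue eDiary completion every evening starting at Day 1 through Day 20". Section 9.3 requires follow-up until an event resolves or stabilises, but for serious events only.

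**The concern.** The event is measured on one clock and the follow-up on another. Healing time runs from tag loss or removal, while the final visit is fixed from the day of banding. Nothing ties the last assessment to the date of loss. The later a tag goes, the less healing time is seen before exit, and for some tags the time seen is shorter than the 14 days that the definition requires.

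This affects a listed safety outcome in a pivotal study of a device meant for over-the-counter sale. The tags least well observed are the slow responders and those the Investigator had to remove. If delayed healing is more frequent in these tags, the loss of information falls where it matters most.

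**Working it through.** The protocol states no prolonged-healing rate, so there is no figure to reproduce. The check is day arithmetic.

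**Inputs**
- Threshold: more than 14 days after loss or Investigator removal (Sections 9.2 and 6.2.6.1).
- Visit 4: Day V, from 30 to 37 (Section 6.2.4).
- Tag loss that counts as success: up to Day 20 (Section 2.2).
- Investigator removal if the tag remains at Visit 3: Day 21 or later (Section 6.2.4, footnote 1).

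**Condition.** With loss or removal on Day L, an unhealed site meets the definition at Visit 4 only if V − L > 14, that is L ≤ V − 15.

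| Visit 4 on Day | Latest loss day at which an unhealed site can be classified |
|---|---|
| 30 | 15 |
| 31 | 16 |
| 32 | 17 |
| 33 | 18 |
| 34 | 19 |
| 35 | 20 |
| 36 | 21 |
| 37 | 22 |

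At the boundary, 30 − 15 = 15 exceeds 14, but 30 − 16 = 14 does not.

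**Reading the table**
- A Visit 4 on Days 35-37 covers every loss up to Day 20.
- A Visit 4 on Days 30-34 leaves some or all losses on Days 16-20 short of the threshold.
- Removal on Day 21 needs Day 36 or 37, and removal on Day 22 needs Day 37.
- Removal on Day 23 needs Day 38, outside the window. Removal on Day 24 needs Day 39.

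**Other scheduled sources.** The diary ends on Day 20, so it reaches the threshold only for losses by Day 5 (20 − 15). Visit 3 on Days 21-24 reaches it only for losses by Days 6-9 (21 − 15 to 24 − 15). For later losses, Visit 4 is the only scheduled assessment.

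**Possible size, on assumptions not in the documents.** Let s be the share of assessed tags lost on Days 16-20. Assume the same true event rate in all tags, no extra visit, and unclassified sites counted as non-events.
- Every Visit 4 on Day 30: observed/true = 1 − s, which is 0.90 at s = 10% and 0.70 at s = 30%.
- Visit 4 spread evenly over Days 30-37 and losses evenly over Days 16-20: the shares of visit days that come too early are 1/8, 2/8, 3/8, 4/8 and 5/8, with mean 0.375. Observed/true = 1 − 0.375s, which is 0.96 at s = 10% and 0.89 at s = 30%.

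These figures only illustrate the range. The protocol gives neither loss dates nor visit dates, and excised tags are not in the calculation.

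**The case against.** The case on the other side has real force on five points.

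**Healed sites.** A reader might infer that every tag lost after Day 15 is unassessable at a Day 30 exit. It is not. A tag lost on Day 18 whose site is healed on the Day 30 photo is a known non-event. The gap is confined to sites still unhealed at Visit 4 with 14 days or fewer elapsed.

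**Unscheduled Visit.** The protocol has a route for a site that worries the Investigator: an in-clinic visit with no fixed window, a limited skin examination and adverse event collection. So it is too strong to say the event cannot be observed. The route does not close the gap, however. It is discretionary, and a site still healing at 10 to 14 days does not yet meet the definition, so a participant may properly be cleared to leave.

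**Bias.** A reader might infer that unclassified tags are counted as event-free and that the rate will be understated. The protocol defines no rate or denominator for this event, and that rule may stand in the SAP, which is not at hand. What remains is that the visit schedule does not secure the observation, and no analysis rule can recover it afterwards.

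**Number of excised tags.** At the planned 60% success, 200 × (1 − 0.60) = 80 tags would not be removed by the device. A reader might take 80 as the number excised too late to assess. It is only an upper bound. Excision is optional, with self-removal of the band as the alternative, and some of the 200 may have been treated under version 1, when Visit 3 fell on Days 11-14. The schedule's footnotes also disagree on when excision is offered: footnote 1 refers to Visit 3 and footnote 3 to Day 10. These need reconciling.

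**Denominator.** Restricting the rate to tags with at least 15 days of follow-up looks like the natural repair. It would drop sites known to have healed in time and keep unhealed sites whose follow-up was extended, which selects on outcome and pushes the rate upward.

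**Conclusion.** The point holds as a mismatch between a definition and a visit window, both fixed in the protocol. At Visit 4, a site still unhealed cannot be classified if the tag went after Day 15 (visit on Day 30), with the limit rising to Day 22 (visit on Day 37). Investigator removal on Day 23 or later cannot reach the threshold at any permitted Visit 4. Because the only further route is discretionary, the event is likely to be under-recorded for late-lost and excised tags.

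The day limits are exact and rest on no assumption. The size of the under-recording cannot be computed from the documents: it depends on loss dates, visit dates and the use of Unscheduled Visits. This is one less common safety item and not the primary endpoint, so the point is a cheap improvement and does not threaten the trial's main result.

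**What to change.** 1. Reconcile the Section 9.2 definition with the timing of Visit 4, and state how Investigator removals on Day 23 or later are to be classified, since the present window cannot reach them.
2. For tags lost on Days 16-20, schedule Visit 4 at least 15 days after loss: from Day 31 for a Day 16 loss to Day 35 for a Day 20 loss. This stays within the existing window. The loss date should be known by Visit 3, when the diary is reviewed, so the date can be set then. Where a subject has two treated tags, the later loss governs.
3. In reporting, count sites healed at Visit 4 within 14 days of loss as non-events. Class as undetermined only sites still unhealed with 14 days or fewer of follow-up. Report their number, and give the rate twice: counting them as no events and as all events. Do not drop every tag with under 15 days of follow-up.

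The cost is a scheduling note and one reporting rule. Some subjects leave the study a few days later, and the safety table gains a small undetermined category.

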9.3. Serious Adverse Event (SAE)

A serious adverse event is any adverse event that leads to:

- a) death
- b) serious deterioration in the health of the subject, users, or other persons as defined by one or more of the following:
 - a. a life-threatening illness or injury, or
 - a permanent impairment of a body structure or a body function including chronic diseases, or
 - c. in-patient or prolonged hospitalization, or
 - d. medical or surgical intervention to prevent life-threatening illness or injury, or permanent impairment to a body structure or a body function;
 - e. fetal distress, fetal death, a congenital abnormality, or birth defect including physical or mental impairment.

Serious adverse events must be reported to the sponsor within 24 hours of coming to the investigator's attention. Any serious adverse event that occurs any time after the participant has signed the informed consent form for the trial, up to the Participant's final trial visit, inclusive, is to be reported through the EDC within 24 hours following when the event was first recognized, discovered, or reported, regardless of severity or relationship to the trial device.

The investigator is to also notify the IRB/EC of the serious adverse event promptly, and according to IRB/EC requirements. Documentation of the serious adverse event reports (using Form FDA 3500A or equivalent) should be submitted to Lindus Health at [contact]. Documentation is to be kept in the investigational site's trial files and is to be checked routinely by the clinical research associate (CRA).

After receipt of a serious adverse event report, the sponsor will notify all appropriate regulatory authorities as necessary, within the required time frames. Written safety reports submitted to

regulatory authorities will be completed by the sponsor with the assistance of the investigator and other site personnel as needed.

Serious adverse events must be followed up by the investigator until resolution or stabilization.

9.4. Causality or Association of the Device with an AE or SAE

When the device caused or was associated with an AE or SAE, the event is an Adverse Device Event (ADE), or Serious Adverse Device Event (SADE), respectively.

9.5. Serious Adverse Device Event Expectedness

A SADE may be anticipated, an anticipated serious adverse device event (ASADE), or unanticipated, an unanticipated serious adverse device event (USADE).

Unanticipated serious adverse device events (USADEs) require expedited reporting to health authorities.

9.6. Device Deficiency

A device deficiency is a failure of the device to meet requirements for identity, quality, durability, reliability, usability, safety, or performance.

Device deficiencies should be documented by the investigator using Form FDA 3500A or equivalent. Form should be submitted to [contact]. Documentation is to be kept in the investigational site's trial files and is to be checked routinely by the clinical research associate (CRA).

10. PROTOCOL DEVIATIONS

A trial related deviation is a departure from the ethically approved trial protocol or other trial document or process (e.g. consent process or IMP administration) or from Good Clinical Practice (GCP) or any applicable regulatory requirements. Any deviations from the protocol will be documented in a protocol deviation form and filed in the trial master file.

A Lindus Health SOP is in place describing the procedure for identifying non-compliances, escalation to the central team and assessment of whether a non-compliance /deviation may be a potential Serious Breach.

